### 9.3. ANKLE AND TOE BRACHIAL INDICES (ABI AND TBI)

Target limb resting ABI and TBI should be performed per hospital standard of care and consistently among all enrolled subjects through completion of the study. Both target limb resting ABI and TBI are required at baseline and follow-up. ABI and TBI values, including respective individual systolic pressure values must be documented in source and recorded on the appropriate electronic case report forms (eCRFs).

To confirm the Wifi Ischemia grade, Transcutaneous oxygen (TcPO2) may be assessed and recorded only if reliable ABI, ankle pressure, or toe pressure are not attainable. However, if TcPO2 cannot be conducted, it will not be considered a protocol deviation.

#### 9.4. DUPLEX ULTRASOUND (DUS) ASSESSMENT

Lower extremity arterial duplex ultrasound (DUS) assessments will be used to determine arterial stenosis as well as Tacked segment patency (Flow/No Flow). The peak systolic blood flow velocity within the Tacks as well as the target lesion will be taken to determine the PSVR.

The DUS exam should be performed per the Time and Events Schedule in **Section 8.1**. DUS exams performed outside of window or not at all will result in a protocol deviation. Duplex ultrasonography and/or angiography should be performed prior to any endovascular intervention during the follow-up period to assess the treated lesion patency. Operators should have experience with DUS and follow the DUS core laboratory acquisition guidelines and specific methods for measuring the blood flow velocities. All scheduled DUS assessments shall be submitted to the respective DUS core laboratory for analysis, in addition to any DUS performed prior to or after any events meeting MALE criteria.

A comprehensive overview for DUS acquisition requirements can be found in the core laboratory manual.

#### 9.5. QUESTIONNAIRES

Both the WIQ and the EQ-5D-3L will be used to assess changes in the patient’s quality of life throughout the duration of this clinical study.

#### 9.6. RUTHERFORD CLASSIFICATION

Rutherford Classification should be assessed for the target limb and consistently among all patients throughout the duration of this clinical study.

See **Section 24** for a description of Rutherford Classifications.

#### 9.7. WIFI CLASSIFICATION

The Wifi Classification is a grading system created by the Society of Vascular Surgery (SVS). This system focuses on the three main factors that impact amputation risk and clinical management: Wound, Ischemia, and foot Infection (Wifi). Each of the three factors are graded on a scale from 0 to 3. The 0 represents none, 1-mild, 2-moderate and 3-severe.

The Wound portion of the Wifi classification is required for all subjects. For inclusion into the study, the subject must have a Wound Grade 0, 1, or “modified 2”. For the purpose of this study only, an additional Wound grade of modified 2 has been added to the SVS Wound table in **Section 23**. The Wound grade “modified 2” permits a deeper ulcer without exposed bone, joint or tendon; or shallow or superficial heel ulcer, without deep tissue involvement or exposed calcaneus. It also permits gangrenous changes limited to digits. In addition, for the purpose of this study, subjects without

 Joseph L. Mills, Sr, MD, [name], David G. Armstrong, DPM, MD, PhD, [name], [name], [name], MPH, and [name], on behalf of the Society for Vascular Surgery Lower Extremity Guidelines Committee, The Society for Vascular Surgery Lower Extremity Threatened Limb Classification System: Risk stratification based on Wound, Ischemia, and foot Infection (Wifi). J Vasc Surg. 2014; Volume 59, Issue 1, Pages 220–234.e2

presence of wound and gangrene should be given a Wifi Wound grade of 0, regardless of their Wifi Ischemia grade.

The Ischemia portion of the Wifi classification is required for all subjects and uses hemodynamic/perfusion criteria (ABI, Ankle Pressure, Toe Pressure or TcPO2) to determine its grade. Subjects are eligible for inclusion regardless of their Wifi Ischemia Grade. The Ischemia Grade should reflect the value obtained using the following hierarchy: Toe Pressure (or TcPO2) being the first, then the highest Ankle Pressure (if TP or TcPO2 is not attained), then ABI (if ankle pressure is not documented). Therefore, it is crucial to follow requirements for these assessments per **Table 8. Time and Events Schedule Section 8.1**.

The Infection portion of the Wifi classification is required for all subjects and is determined by clinical observations of infection. Subjects must have an Infection Grade of 0 or 1 to be eligible for enrollment.

See **Section 23** for Wifi classification tables.

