**Table 11. Ischemia Grading**

! Ischemia	Hemodynamics/perfusion: Measure TP or TcPO2 if ABI incompressible (>1.3)			
	SVS grades 0 (none), 1 (mild), 2 (moderate), and 3 (severe).			
Eligible to Enroll	Ischemia Grade	ABI	Ankle Systolic Pressure	TP, TcPO 2
Yes	0	≥0.80	>100 mm Hg	≥60 mm Hg
Yes	1	0.60 - 0.79	70-100 mm Hg	40-59 mm Hg
Yes	2	0.40 - 0.59	50-70 mm Hg	30-39 mm Hg
Yes	3	≤0.39	<50 mm Hg	<30 mm Hg

ABI, Ankle-brachial index; PVR, pulse volume recording; SPP, skin perfusion pressure; TP, toe pressure; TcPO2, transcutaneous oximetry.

Patients with diabetes should have TP measurements. If arterial calcification precludes reliable ABI or TP measurements, ischemia should be documented by TcPO2, SPP, or PVR. If TP and ABI measurements result in different grades, TP will be the primary determinant of ischemia grade.

Flat or minimally pulsatile forefoot PVR = grade 3.

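### When neither toe pressure nor TcPO2 is obtained, Section 9.7 lets the WIfI ischemia grade rest on an incompressible ankle pressure or ABI, in conflict with Table 11, and no rule keeps the measure the same between visits

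*Combined protocol and SAP*

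**What the plan says.** Section 9.7 requires an ischemia grade for every subject and sets a three-step order. Toe pressure and TcPO2 share the top step. Below that, the order runs "then the highest Ankle Pressure (if TP or TcPO 2 is not attained), then ABI (if ankle pressure is not documented"). It carries no condition on compressibility.

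Table 11 (Section 23) gives the cut-offs. Grade 0 is ABI of 0.80 or more, ankle pressure above 100 mm Hg, or toe pressure/TcPO2 of 60 mm Hg or more; the ABI and ankle entries have no upper limit. Its header nevertheless says "Hemodynamics/perfusion: Measure TP or TcPO2 if ABI incompressible", with incompressible meaning above 1.3. A note adds "If arterial calcification precludes reliable ABI or TP measurements, ischemia should be documented by TcPO 2 , SPP, or PVR", and another says "If TP and ABI measurements result in different grades, TP will be the primary determinant of ischemia grade".

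Section 9.3 says TcPO2 "may be assessed and recorded only if reliable ABI, ankle pressure, or toe pressure are not attainable", and that if it cannot be done "it will not be considered a protocol deviation". Footnote 10 to Table 8 names non-compressible arteries and prior digital amputation as reasons why a baseline ABI or TBI may be unattainable, asks for an eCRF note, and leaves TcPO2 optional. Footnote 12 excuses follow-up assessments prevented by amputation. SPP and PVR appear in neither Table 8 nor the Section 9.7 order.

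Changes in WIfI classification and in ABI/TBI are observational endpoints followed through 36 months (Section 19.5), summarized descriptively (Section 19.8.4).

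**The concern.** The two passages give different answers for the same limb. Where calcification has made the ankle artery incompressible and no toe pressure or TcPO2 exists, Section 9.7 leads to a grade from the ankle value, while Table 11 treats an ABI above 1.3 as needing another measure. A falsely high ankle reading always points toward less ischemia.

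The second problem is change over time. The measure behind the grade may differ between visits. Toe loss is foreseeable here: gangrene limited to the digits is eligible (Table 10), planned simple digital amputation is permitted (exclusion criteria 4, 7 and 9), and unplanned digit amputation is itself an endpoint. If the measured toe is lost and TcPO2 is not done, the grade passes from toe to ankle, and a bad outcome can appear as better perfusion. In a single-arm study no control group would expose such an artefact. The ABI change summary has a related gap, since no rule deals with values above 1.3.

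**Working it through.** No design figure depends on this rule, so there is nothing of the plan's to reproduce. The check traces the rule and then asks what the pilot (Section 4.2, Table 4) can say about frequency.

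**1. The rule on one illustrative limb** (invented values). No toe pressure or TcPO2; ankle pressure 180 mm Hg; ABI 1.4, which implies a brachial pressure of 180/1.4 ≈ 129 mm Hg.
- Section 9.7: the first step is empty; at the second, 180 > 100 gives grade 0. The third would agree, since 1.4 ≥ 0.80.
- Table 11: 1.4 > 1.3, so toe pressure or TcPO2 is called for.
- The rule that toe pressure prevails over ABI does not help when toe pressure is absent.

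Section 24 computes ABI from the higher of the two ankle pressures. The highest ankle pressure and the ABI therefore share one reading, and an ABI above 1.3 flags both.

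**2. Effect of switching measure.** The extreme is a toe pressure below 30 mm Hg (grade 3) followed by an ankle pressure above 100 mm Hg (grade 0), a shift of three levels.

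For a more typical limb, take the pilot safety-sample medians, ABI 0.94 and TBI 0.47. Brachial pressure B is not in the documents; assume 110 to 160 mm Hg.
- Ankle pressure 0.94 × B exceeds 100 when B > 100/0.94 = 106.4.
- Toe pressure 0.47 × B is below 60 when B < 60/0.47 = 127.7.
- For B from 110 to 127, toe pressure is 51.7 to 59.7 (grade 1) and ankle pressure 103.4 to 119.4 (grade 0): one level.
- For B from 128 to 160, both give grade 0: no shift.

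**3. What the pilot shows.**
- TBI missing: 35 − 24 = 11, and 11/35 = 31.4% (safety sample); 32 − 23 = 9, and 9/32 = 28.1% (performance sample).
- All 35 limbs were Rutherford 4 or 5 (4 + 31). The median ABI of 0.94 is the 18th ordered value, so at least 18/35 = 51% had an ABI in the grade 0 range.
- The maximum ABI was 1.9, so at least one value exceeded 1.3. The mean of 0.95 is over n = 35, so that value was included.
- Rough normal approximation to the share above 1.3: safety sample z = (1.3 − 0.95)/0.42 = 0.83, about 20%; performance sample z = (1.3 − 0.91)/0.41 = 0.95, about 17%. Normality is an assumption.

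**4. What cannot be computed.** The number misgraded requires limbs that lack both toe pressure and TcPO2, have an incompressible ankle artery, and are ischemic. The pilot gives separate ABI and TBI summaries, no pairing within subject, no TcPO2 data and no reasons for missing TBI.

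**The case against.** The strongest reply is that the documents do address incompressibility. Table 11 tells sites what to measure and says that patients with diabetes should have toe pressure; Section 9.3 speaks of reliable readings; footnote 10 counts non-compressible arteries among the reasons an ABI is unattainable. Read together, the illustrative limb should not be graded from its ankle pressure. This is a fair reading, but it is not secured. Section 9.7 states the operative order without the caveat, requires a grade for everyone, and offers no way to withhold one. The alternatives in Table 11 are either optional or unscheduled.

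Several stronger readings are tempting and do not stand:
- A reader might infer that missing toe pressure alone triggers the fallback. It does not: TcPO2 shares the first step, so both must be missing.
- A reader might carry the pilot's 31% over to 73 of 232 subjects here. That figure is pilot TBI missingness under another protocol; this protocol requires both ABI and TBI at baseline and follow-up.
- A reader might take the 51% with ABI in the grade 0 range as a misgrading rate. ABI is the last step in the order, and no data show those values to be false.
- A reader might treat a three-level shift as typical. The pilot medians imply one level at most.

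It is also true that toe loss is visible elsewhere (unplanned digit amputation, and the amputated category of wound progress), that a simple digital amputation need not remove every measurable toe, and that the plan nowhere labels a fall in grade as improvement. Finally, excluding calcified or toe-loss limbs from change summaries is informative. That objection stands, and it shapes the fix.

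**Conclusion.** The conflict between Section 9.7 and Table 11 is real and must be reconciled. When toe pressure and TcPO2 are both absent, some ischemic limbs can be graded 0, and a change of measure after toe loss can appear as an improved grade. The direction is toward less apparent ischemia; the size is unknown. The pilot's 11 of 35 missing TBI is only an indication that the situation may arise, and its maximum ABI of 1.9 shows that values above 1.3 occur and enter means. The calculated grade shift rests on an assumed brachial pressure of 110 to 160 mm Hg and on medians that need not come from the same limb.

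The consequence is confined to the descriptive WIfI and ABI change endpoints. Ischemia grade does not affect eligibility, and the primary endpoints, 6-month patency and sample size are untouched. This is a worthwhile, inexpensive improvement, not a threat to the trial's main conclusions.

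**What to change.** - Reconcile Section 9.7 with Table 11, including whether SPP and PVR count and where they would be recorded. For the analysis, enter a grade that would rest only on an ankle pressure or ABI with ABI above 1.3 as *not gradable*, and amend the Section 9.7 requirement for a grade in all subjects to match.
- Record which measure produced each ischemia grade.
- Report change in ischemia grade for visit pairs using the same measure, beside the all-pairs summary, with counts of subjects whose measure changed and of those whose toe measure was lost to amputation.
- Report ABI change with and without values above 1.3, with the number of such values.

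The cost is wording in Section 9.7, one added data item (the measure used) and extra columns in descriptive tables; Section 9.3 already has the individual systolic pressures in the eCRF. The downside is fewer subjects in the restricted summaries. Those left out are calcified or toe-loss limbs and not a random subset, so neither version should be shown without the other and the counts.

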#### 9.8. WOUND ASSESSMENT

An assessment of existing and/or new wound(s) is to be performed per **Table 8. Time and Events Schedule Section 8.1**. Wounds should be classified as: Healed, Improved, Unchanged, Worsening, Amputated or New (If applicable). If, at the time of any follow-up visit, a patient's wound is dressed and per PI discretion the dressing should not be removed, this should be documented and will not be considered a deviation.

All assessments shall be accompanied by a photograph of the wound(s) that includes a ruler. These photographs shall be part of the subject's study file.

#### 9.9. X-RAY ASSESSMENT

An X-Ray assessment will be performed at the 12-month follow-up visit to assess Tack implant integrity for all subjects in whom at least one Tack implant was placed during the index procedure. If an X-ray is performed prior to the 12-month visit and is within the 12-month visit window and all Tacks are imaged, this may be used in lieu of the X-ray required at the 12-month visit.

A comprehensive overview of procedural requirements for X-Ray assessments can be found in the core laboratory manual.

### 10. SCREENING PROCEDURES

All subjects presenting to the institution with PAD and/or known popliteal (P2 and P3) and/or below-the-knee artery disease requiring balloon angioplasty will be screened for initial eligibility. A trained member of the research team shall perform a preliminary evaluation of the potential subject's medical history and screen for initial eligibility. Only assessments consistent with the institution's standard of care may be performed prior to obtaining a signed consent form. If during the pre-screening the subject is found to meet one or more exclusion criteria, the subject would be considered a "pre-screen failure". No further action shall be taken for pre-screen failure subjects. If determined eligible per initial inclusion criteria, the subject will be approached by qualified and trained research staff and informed about this study through the informed consent process.

## 10.1. OBTAINING INFORMED CONSENT

All sites shall comply with 21 CFR 50, provisions of ICH E6 Good Clinical Practices (GCPs), local institutional review board (IRB)/ethics committee (EC) policy and all applicable local regulations for obtaining Informed Consent. Written informed consent using the most current IRB/EC-approved ICF at the time of consent will be obtained for all subjects **prior** to any study-specific screening/baseline tests or procedures are performed. This does not include those procedures or tests that are obtained in the normal course of the subject's non-study related care and prior to undergoing the study procedure, but shall include previously performed tests that may need to be repeated to determine eligibility.

All subjects shall possess the ability to understand the information contained in the informed consent form. Subjects will have the study procedures explained in a manner as non-technical as possible, including the risks, benefits and follow-up requirements. If the subject agrees to participate in this study, the subject will personally sign and date the ICF. If a subject possesses the ability to understand the informed consent process and participation in study, but due to physical inability cannot sign the ICF, an impartial witness may sign the ICF on behalf of the subject. Non-English speaking subjects may only be enrolled if they sign an IRB/EC approved and certified translated informed consent form document reflective of his/her spoken language.

Once all required parties have signed the ICF, subjects will receive copies of their signed informed consent documentation.

## 10.2. SCREENING SUCCESS AND FAILURE CRITERIA

Final eligibility of a subject will occur during the Index Procedure. Subjects must provide prior informed consent no greater than 30 days prior to the index procedure. Every effort will be made to ensure eligibility of the participants prior to enrollment. If no angiographic exclusion criteria are met after pre-enrollment angioplasty, subjects will be considered eligible for enrollment. If at any point prior to or just after pre-enrollment angioplasty, an angiographic exclusion criterion is met, subjects will not be considered eligible for enrollment and will be documented as "angiographic screen failures". No further follow-up will be required for these subjects, however; reason for angiographic failure shall be documented by the site into a screening log. Both limbs may be considered for enrollment if all study-required timeframes per the inclusion/exclusion criteria are met. If 30 days have passed since the subject signed an informed consent form, the subject should be re-consented.

## 11. BASELINE EVALUATION

### 11.1. BASELINE ASSESSMENTS

The following assessments will be performed during baseline evaluation. These examinations and tests will be used both to screen for eligible subjects and provide baseline information for those subjects who meet study criteria. All assessments must be completed no more than 30 days prior to undergoing the index procedure, except for the urine pregnancy test which must be completed no more than 7 days prior to the index procedure with a negative result prior to receiving treatment.

- Demographic information and medical history including risk factors

- Brief physical examination
  - Including height and weight
- Target Limb Resting ABI
- Target Limb Resting TBI
- Target Limb TcPO2 (to confirm Wifi Ischemia score only if ABI, ankle pressure, or toe pressure cannot be attained)
- Rutherford Classification
- Wifi Classification
- Wound Assessment
- WBC, Platelet count
- PT & INR (if on chronic warfarin therapy)
- Urine pregnancy test if female of child-bearing age (within 7 days of procedure)
- EQ-5D-3L
- Walking Impairment Questionnaire (WIQ)
- Study medications (antiplatelet/anticoagulants)

## 12. STUDY MEDICATIONS

See **Table 9** below for Study Medications. Pre-procedural, intra-procedural and post-procedural medications will be recorded in the eCRF.

**Table 9: Recommended Study Medications**

Medication	Pre-Procedure	Intra-Procedure	Post-Procedure
Aspirin	Loading dose if required, per institutional standard of care if not on chronic antiplatelet therapy	N/A	81-325 mg/QD indefinitely is recommended
Thienopyridine Class Agent 	Loading dose if required, per institutional standard of care if not on chronic antiplatelet therapy	N/A	75 mg/QD for a minimum of one month recommended 
Heparin	Dosage per institutional standard of care.	Achieve anticoagulation per hospital / institution standard of care 	N/A

 Recommended Thienopyridine class agents include Clopidogrel, Ticlopidine or Prasugrel.

 Recommended daily dose for Clopidogrel. Respective regimen should be prescribed for other thienopyridine agents per Investigator discretion.

 An Activated Clotting Time (ACT) of ≥250s is recommended.

## 13. INDEX PROCEDURE

### 13.1. INDEX BASELINE ANGIOGRAM

The Index Baseline Angiogram will be performed before Pre-Enrollment Balloon Angioplasty in order to assess baseline angiographic eligibility for inclusion as described in **Section 13.1.2** below. The angiogram is to be performed as per guidelines established by the independent core laboratory. Index procedure angiograms performed for all enrolled subjects will be reviewed by

the core lab for identification of post-PTA dissections and associated type, as outlined in the angiographic core lab protocol.

All data that is required to be recorded during the Index Procedure is reflected in the index procedure interval eCRFs within the EDC. Required measurements and data listed in following sections are not exhaustive of all data that is required. Therefore, the required data should be reviewed in advance of the procedure to ensure it is understood and captured appropriately. The CRF Completion Guidelines contain instructions for data entry and should be referenced as necessary.

#### 13.1.1. PREPARATION

Procedural techniques will be in accordance with the institutional standard of care for balloon angioplasty of the popliteal (P2 and P3) and below-the-knee arteries.

All subjects should receive the appropriate antiplatelet and anticoagulant therapy per **Table 9**. Study Medications above (**Section 12**).

A radiopaque ruler is placed directly on the subject's target limb under the sterile drapes according to the angiographic core lab imaging protocol. In any later angiographic assessments, the same ruler placement should be used to identify the treatment location.

#### 13.1.2. BASELINE ANGIOGRAPHIC REQUIREMENTS

Baseline angiographic measurements of the target lesion and target vessels (visual estimate) shall be captured to determine eligibility and include, but are not limited to the following:

- Target Lesion(s) details including Vessel location(s), Ruler location(s), Lesion length(s) (normal to normal), and pre-PTA %DS
- Lesion type(s) (De novo or restenotic)
- Reference Vessel Diameter(s) (proximal and distal)
- Inflow artery patency
- Normal artery branching and/or target vessel reconstitution
- Absence of thrombus

#### 13.2. PRE-ENROLLMENT BALLOON ANGIOPLASTY (TREATMENT PTA)

All consented subjects undergoing balloon angioplasty for possible enrollment into this study shall receive PTA treatment with a standard balloon.

The recommendations for balloon inflation are as follows:

- The operator should select a balloon diameter that can be inflated to a ratio of 1:1 relative to the target lesion proximal RVD
- The length of the balloon should be appropriate for the lesion length, fully covering the lesion. When possible, a single balloon should be selected that extends across the entire lesion.

- Balloon Inflation: Inflate the balloon and maintain inflation at the specified 1:1 diameter for a minimum of 60 seconds total

Please refer to the Instructions for Use (IFU) for detailed instructions regarding Pre-Enrollment Balloon Angioplasty inflation recommendations.

